4. The patient will have standing radiographs of the affected knee.

Evaluation at the time of surgery:

At the time of surgery, the patient will be randomized to treatment with either an arthroscopic partial meniscectomy or arthroscopic lavage. Randomization will be done by opening a sealed envelope in the operating room prior to the procedure. To ensure balanced numbers in the two surgical conditions, especially at the time of the interim look, randomization will be done by permuted blocks of size 10, thereby ensuring 5 patients in each group at every increment of 10 enrollees.

Upon initiation of the surgery, a sample of synovial tissue and synovial fluid will be obtained for biochemical analysis. During the operation, the status of the knee joint will be documented. This will include classifying the degree of chondromalacia according to the Outerbridge classification in all three compartments of the knee, and documenting the geometry and pattern of meniscus tear type. Video and photographs will be taken to assist with this documentation and will be stored in a secure manner.

During the operation, the meniscus will be carefully probed. If a large unstable flap of tissue can be displaced into the articulation (such as a bucket handle tear) this torn fragment will be debrided regardless of the result of randomization. This will be done as it is widely believed that it is inappropriate to leave such an unstable tear untreated. Any other tear types that do not result in an unstable flap that can be displaced into the articulation will be either retained or debrided, depending on the result of randomization.

All postoperative contact from this point forward will be made by study personnel who were not involved in the surgery and who do not have knowledge of the randomization result.

At 2 weeks and 6 weeks:

The patient will have regularly scheduled clinic visits at 2 and 6 weeks that are not a part of the study but are just a part of the routine postoperative care of knee arthroscopy patients. Postoperative care as deemed necessary by the treating physician will be provided and could include pain and/or anti-inflammatory medications. Physical therapy is rarely needed. All provided treatments will be recorded in the chart.

Evaluation at 3 months:

1. The patient will fill out WOMET and WOMAC surveys.
2. The patient will undergo gait analysis.
3. The patient will have an MRI of the knee

Evaluation at 6 months:

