74 subjects will thus be needed to complete the trial. Over a one year period we will expect to have a 10% lost to follow-up rate. We will thus plan to enroll 82 subjects into the study. With a 70% recruitment rate we will need to have 117 candidate patients for this study. In calendar year 2011, we performed 66 arthroscopic meniscectomies at our facility. Assuming that 70% of these cases involved stable degenerative tears, we would have 46 candidate patients per year. It would thus take us approximately 2.5 years to recruit enough patients for the study if we were to operate at last year's rate. We presently have approximately 100 patients for knee arthroscopy on our waiting list for surgery, which makes it likely that we could accomplish this goal more rapidly.

Hypothesis 1b: Should we fail to find a difference in 12 month WOMAC scores, we will test the hypothesis that the WOMAC scores in the arthroscopy and lavage condition are at least as good as (non-inferiority) the meniscectomy by setting "d" the largest difference in WOMAC scores which we consider to be clinically meaningless to 15% of baseline, or 194 points. We will then calculate 90% confidence limits for the difference in means for the two groups and determine whether these confidence limits lie within the -194 to 194 point interval. Since there is no danger to patients if this hypothesis is found to be true, this hypothesis will not be subject to an interim analysis. We will assume that the standard deviation of the means is 392. With these numbers, the sample size of 74 and alpha = .10 and yields power = .80.

Aim 2: *To test the functional effect of arthroscopic meniscectomy in the setting of a degenerative meniscus tear.*

Hypothesis 2: Subjects randomized to arthroscopy and meniscectomy will have greater changes in tibio-femoral rotation, knee adduction moment, and knee flexion moment at 12 months following surgery when compared to subjects randomized to arthroscopy and lavage.

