Calculations were performed to estimate the necessary sample size for the endpoints of Aim 2 of changes in tibio-femoral rotation, knee adduction moment, and knee flexion moment. In order to keep the family-wise error rate at .05, each comparison will be made with an independent sample t-test with alpha = 0.0167. To reject the null hypothesis that changes in tibio-femoral rotation will not differ between the intervention (meniscectomized) knees and control (non-meniscectomized knees), data from a similar study performed in our laboratory evaluating tibial rotation using the same techniques between meniscectomized knees and intact knees was used (Netravali et al., 2010). In that study, we found a 3.2 degree difference in tibio-femoral rotation in meniscectomized knees when compared to intact contralateral knees using a t-test. The standard deviation of the measurements in the meniscectomized knees was 3.8 degrees. Thus, to detect a difference of 3.2 degrees tibio-femoral rotation in the meniscectomized group

versus no change in the intact group, with an alpha of 0.0167 and 74 total patients, power of 87% will be achieved.

In addition, we would be interested to detect a change in peak adduction moment of about 10% of baseline value. This corresponds to a change of 0.35%BW*ht (Netravali et al., 2010). Prior work looking at changes in knee adduction moment with intervention find a standard deviation of the difference in peak adduction moment with the intervention to be 0.35%BW*ht. With an alpha of 0.0167 and 74 total patients, power of 94% will be achieved.

Finally, we are interested in detecting a change in peak flexion moment of about 10% baseline value. This corresponds to a change of 0.3%BW*ht (Netravali et al., 2010). Assuming a standard deviation of the flexion moment of approximately 0.35%BW*ht. With an alpha of 0.0167 and 74 total patients, power of 89% will be achieved.

Missing Data:

All analyses will be on the intent-to-treat sample. To address missing data at 1 year (and other time points), we will use a multiple imputation strategy that minimizes potential attrition bias. Ten datasets will be imputed with draws from the theoretical complete data distribution using the Multivariate Imputation by Chained Equations (MICE) program implemented in the R statistical language. All analyses with these data will be conducted on the imputed datasets and combined to yield the final parameter estimates and inferences.

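### Hypothesis 1b (non-inferiority of lavage) rests on the intent-to-treat sample alone, with no supporting analysis that accounts for meniscectomy received by lavage patients before month 12

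*Combined protocol and SAP*

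**What the plan says.** Hypothesis 1b is conditional on 1a: "Should we fail to find a difference in 12 month WOMAC scores, we will test the hypothesis". What is then claimed for lavage, if 1b succeeds, reads: "the WOMAC scores in the arthroscopy and lavage condition are at least as good as (non-inferiority) the meniscectomy". The margin d is "the largest difference in WOMAC scores which we consider to be clinically meaningless to 15% of baseline, or 194 points". For the decision, "We will then calculate 90% confidence limits for the difference in means for the two groups", and the team will "determine whether these confidence limits lie within the -194 to 194 point interval".

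The Missing Data section fixes the analysis set for the whole plan: "All analyses will be on the intent-to-treat sample". Multiple imputation is specified for missing values. A WOMAC score obtained after a later operation is not missing, so imputation does not touch it.

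The only other Aim 1 analyses are t-tests on change scores (under Hypothesis 1a) and covariate or propensity-score adjustment for imbalance (under Randomization). Neither uses treatment received.

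On later care, the section for the 2-week and 6-week visits says "Postoperative care as deemed necessary by the treating physician will be provided". It adds that treatments are charted, but no analysis draws on that record. The documents do not mention a meniscectomy after the index operation: they give no rule, no expected rate and no data handling.

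**The concern.** Everyone enrolled has had mechanical symptoms for at least three months despite conservative care and is already booked for meniscectomy (Patient Selection). Patients assigned to lavage keep the torn tissue unless an unstable flap is found. Some whose symptoms continue could have the meniscus resected during the twelve months before the endpoint, and under intent-to-treat their scores after that operation count as lavage scores.

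In a superiority test such as 1a, making the arms alike costs power and is otherwise conservative. In 1b the direction reverses, because similarity is what counts as success. The Background presents an ineffective surgery as an important area for cost savings, and a positive 1b would be the main support for that reading. It would be weak support if part of the similarity arose because lavage patients had received the comparator.

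**Working it through.** **Inputs.** Margin 194 (15% of the pilot mean of 1296 is 194.4). SD 392, 37 per arm and a 1a target difference of 260, all from Aim 1. Two-sided 90% limits, both required within ±194, from Hypothesis 1b. The crossover share c is not in the documents; 0 to 30% is an assumed range.

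**Standard error.** SE = 392 × √(2/37) = 91.1, with 72 degrees of freedom.

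**The plan's own figure.** The stated 1b power is .80 with 74 subjects. At one-sided 0.10 and a true difference of zero: Φ(194/91.1 − 1.282) = Φ(0.847) = 0.80, so the figure reproduces. It does not match the written rule. Two-sided 90% limits correspond to one-sided 0.05, giving Φ(2.129 − 1.645) = 0.686 for one limit and 2 × 0.686 − 1 = 0.371 for both. That is a separate matter, but the written rule is the one used below.

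**Dilution.** If a share c of lavage patients reach the meniscectomy-arm mean by month 12, the expected intent-to-treat difference is D × (1 − c), where D is the true deficit.

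**Chance that both 90% limits lie within ±194** (two-sample t interval, SD estimated):

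| Crossover c | D = 194: expected difference | Meets 1b | D = 260: expected difference | Meets 1b |
|---|---|---|---|---|
| 0% | 194.0 | 4.5% | 260 | 0.9% |
| 10% | 174.6 | 6.7% | 234 | 1.7% |
| 20% | 155.2 | 9.5% | 208 | 3.3% |
| 30% | 135.8 | 13.0% | 182 | 5.8% |

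**Does failure of 1a add to this?** The 90% half-width is 1.666 × 91.1 = 151.9, so meeting 1b needs an observed difference within about 194 − 151.9 = 42 points. Significance in 1a needs about 1.96 × 91.1 = 179 points. For one trial to satisfy both, the estimated SE would have to be below 194/(1.96 + 1.666) = 53.5, against an expected 91.1. Simulations of 1,000,000 trials at each of several true differences found none that met both. Every trial that passes 1b has therefore already failed 1a. Crossover lowers 1a power at 260 from 0.81 to 0.73, 0.63 and 0.51 at 10%, 20% and 30%, but this produces no additional false 1b conclusions beyond those in the table.

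**The case against.** The strongest reply is that the premise is not in the documents. No section mentions reoperation. The passage on postoperative care concerns routine visits and goes on to name medication and, rarely, physical therapy. Patients stay blinded until the study ends, and postoperative contact is by staff who do not know the allocation; both may limit crossover. There is also a waiting list of about 100 for knee arthroscopy, so relisting, reoperation and full recovery by month 12 may be uncommon. A patient reoperated late may not have gained the full benefit, which would weaken or even reverse the bias. All of this stands. It limits the likely size but does not remove the gap, because nothing in the plan would show whether crossover had occurred or mattered.

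It can also be said that intent-to-treat answers a legitimate policy question: lavage first, with later surgery if needed. That is right, and it is why intent-to-treat should be kept.

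A reader might infer several stronger things that the documents do not support:

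- **That crossover will be common.** No rate is given, and 20–30% has no basis in the plan.
- **That about 25% crossover would let a 260-point deficit pass.** At c = 25.4% the expected difference reaches 194 (260 × 0.746), but the rule needs both limits inside the margin. The chance of that is 4.5%.
- **That failure of 1a, as the trigger for 1b, compounds the bias.** The working shows it adds nothing.
- **That 1b should be gated on carrying forward the last pre-reoperation score in the lavage arm only.** This penalises one arm and can bring forward a preoperative score. With truly equal arms, replacing 4 of 37 lavage values by values 561 points worse (the pilot's one-year gain) lowers the 1b pass rate from 36% to 24%, and replacing 7 of 37 lowers it to 14%. At half that gap the rates are 32% and 29%.
- **That Aim 2 is biased in the same way.** Hypothesis 2 compares groups as randomised and looks for a difference, so dilution there is conservative.

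**Conclusion.** The concern holds as a gap in the plan, not as an error in choosing intent-to-treat. Hypothesis 1b has a single analysis set, and the bias from later meniscectomy in the lavage arm would favour its success if meniscectomy is truly better. At the margin, the false-claim rate goes from 4.5% to about 6.7% at 10% crossover, roughly doubles at 20% and nearly triples at 30%. At the plan's clinically important difference of 260 it stays below 5% up to about 25% crossover and is 5.8% at 30%.

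These figures rest on an assumed crossover range, full benefit for crossovers by month 12, SD 392 and 37 analysed per arm. If no lavage patient has a later meniscectomy, the gap has no consequence. It merits an inexpensive improvement and does not call for a change in the primary analysis.

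**What to change.** 1. Record the date and type of any further surgery on the index knee through month 12, in both arms, on a study form and not only in the chart. Report it by arm.
2. Keep intent-to-treat for 1b. Pre-specify beside it one supportive analysis that accounts for post-randomisation meniscectomy and applies the same rule to both arms. Options are a per-protocol set, or WOMAC values after reoperation set to missing and multiply imputed under stated assumptions, including one less favourable to lavage. State how unstable flaps debrided at the index operation, which the protocol requires whatever the assignment, are classified.
3. State that the non-inferiority conclusion will be described as robust only if the two analyses agree.

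Patient care does not change. The cost is one form item, a paragraph in the statistical section and a little more analysis. Precision falls in the supportive analysis: excluding about 10% or 20% of lavage patients (37 versus 33, or 37 versus 30) raises the SE from 91.1 to 93.9 or 96.3. One-limit power at one-sided 0.05 then goes from 0.69 to 0.66 or 0.64. A per-protocol set can also carry selection bias of its own, which is why it sits beside intent-to-treat and does not replace it.
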